#### Additional Exploratory Analyses

We also propose several exploratory analyses that will investigate how relationships between the symptom experience, depression, and health-related quality of life change over time. These analyses will guide subsequent applications of our intervention. For example, an understanding of the time course by which symptoms and depression effect quality of life will help target assessments and treatments focused on quality of life outcomes to this time frame. The exploratory analyses will address two questions:

Question 1: How much do changes in potentially modifiable factors, such as symptom severity and burden and depression, explain variation in quality of life? We hypothesize that changes in modifiable factors over time explain the largest amount of variance in quality of life over time. The analysis (SAS Proc Mixed) will utilize the change from baseline in quality of life (as measured by the KCCQ quality of life subscale) at 3, 6 and 12 months as the outcome. We will estimate the proportion of the variance explained by baseline demographic variables (e.g. age, gender); baseline measures of disease severity (e.g. ejection fraction, BNP); and changes in modifiable factors (symptom distress and severity, depression, attitudes about impairment and spiritual well-being).

Question 2: How does the strength of the association between changes in quality of life and changes in the modifiable and unmodifiable factors vary over time? We hypothesize that the modifiable (particularly the psychological) associations will increase and the unmodifiable will decrease over time. These hypotheses will be tested by adding interactions with time to the models employed to answer question 1.

**Aim 2. Evaluate whether the intervention influences quality of life indirectly through effects on symptom severity and depression.** This aim will examine our conceptual model using a mediation analysis. The data gathered in the clinical trial described in Aim 1 will be used to complete this aim.

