18. Demographics/Study Form: Age, gender, race and ethnicity, education level, and clinical variables will be determined at the enrollment visit from the electronic medical record and patient self-report. NYHA classification, etiology of HF, most recent ejection fraction, and BNP or NT-pro BNP will be documented. Medical history (including comorbidities), current medications, and number/reasons for hospitalizations in the previous two years will also be collected at the enrollment visit. At the final study visit, patients will be asked to relate *interim events* at follow-up visits, including hospitalizations with cause and emergency department (ED) visits, the reasons for them, and for permission to obtain medical records relevant to such events. Medications will be documented again.

19. Interim events: Over the 12-month study period for each patient, the following events will be assessed through medical record review to supplement patient report: hospitalization (with cause), outpatient/ED visits, and mortality. Vital status will also be ascertained via the VA Vital Status File and the National Death Index.

20. Program Evaluation: Participants in the intervention group will be asked for their feedback regarding the helpfulness of the intervention portion of the study after all of the outcome measures have been completed.

Process measurement

We will document study processes to facilitate replication and incorporation in dissemination manuals if the intervention is successful and to provide insights for future interventions if not successful. Process measurement will also generate insight into which aspects of the intervention were most effective, and will allow accounting intervention resource use. Process measurement will include: (1) tracking of nurse and social worker contacts with patients, including number, time spent, and reason; (2) tracking of adherence to the intervention protocol using a study form that examines whether or not study protocol actions were completed, as measured by medical record review; and (2) accounting of medication and testing recommendations by the collaborative care team and proportion executed.

Protocol: Improving Symptoms and Quality of Life in Chronic Heart Failure

PI: [name],

COMIRB #: 11-0969

Caregiver Outcomes and Planned Study Visits

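### Exploratory Question 1 ranks baseline-only disease severity against concurrent change scores, which tilts the comparison towards its own hypothesis

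*Protocol*

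**What the plan says.** All of this is in the protocol, Data Analysis Plan, Aim 1, under Additional Exploratory Analyses, read against the list of patient measures.

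**Question 1.** The outcome is a change score: the model "will utilize the change from baseline in quality of life (as measured by the KCCQ quality of life subscale) at 3, 6 and 12 months". Variance is to be apportioned among three blocks: baseline demographics; "baseline measures of disease severity (e.g. ejection fraction, BNP"; and "changes in modifiable factors (symptom distress and severity, depression, attitudes about impairment and spiritual well-being". The hypothesis is a ranking: "We hypothesize that changes in modifiable factors over time explain the largest amount of variance in quality of life over time".

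**Question 2.** It asks "How does the strength of the association between changes in quality of life and changes in the modifiable and unmodifiable factors vary over time". The hypothesis is "We hypothesize that the modifiable (particularly the psychological) associations will increase and the unmodifiable will decrease over time". The method is "These hypotheses will be tested by adding interactions with time to the models employed to answer question 1".

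**What is collected.** Item 18 (Demographics/Study Form) deals with the enrollment visit and says "NYHA classification, etiology of HF, most recent ejection fraction, and BNP or NT-pro BNP will be documented". For the final visit the same item names interim events and medications. Table 6 marks the Demographics/Study Form at baseline and again at 12 months, and the questionnaires at all four visits. None of the patient instruments in Table 7 or the numbered list is described as measuring attitudes about impairment. The nearest, the Sheehan Disability Scale, is described as a measure of functional disability.

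**The concern.** The Question 1 hypothesis is about which block explains most, but the blocks enter the model in different forms. The outcome is a change. Symptoms, depression and spiritual well-being are entered as changes over the same follow-up. Disease severity is entered as one fixed starting value. A starting value generally explains less of a later change than a factor whose own movement over that period is in the model, even if the two factors matter equally. A larger share for the modifiable block could therefore reflect how the predictors were entered rather than how much they matter.

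This bears on interpretation. The section says these analyses will guide later use of the intervention, and Background and Significance presents the relative impact of different predictors of quality of life as something the study will contribute.

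Two smaller inconsistencies sit beside it. The wording of Question 2 does not match its model, and one named predictor in Question 1 has no instrument.

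**Working it through.** The protocol states no figure for this comparison, so there is none to reproduce. The direction and possible size of the tilt can be derived from a simple model in which every value is assumed.

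**Set-up.** Let S be disease severity and X be symptoms. Let quality of life at time t be Q_t = −S_t − X_t + e_t. S and X carry equal weight, are independent, have variance 1 at both times (stationary), and each has correlation rho with its own baseline. The errors e are independent with variance 1. Write d for the change from baseline to one follow-up visit.

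**Variance of the outcome.** Var(dS) = Var(dX) = 2(1 − rho), and Var(de) = 2. So Var(dQ) = 2 + 4(1 − rho).

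**Severity entered at baseline.** Cov(S_0, dQ) = 1 − rho, so R² = (1 − rho)² / Var(dQ).

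**Symptoms entered as a change.** Cov(dX, dQ) = −2(1 − rho), so R² = 4(1 − rho)² / [2(1 − rho) Var(dQ)] = 2(1 − rho) / Var(dQ).

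**Ratio.** Dividing the first by the second gives (1 − rho)/2. The error variance cancels.

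| Assumed rho | R², baseline severity | R², change in symptoms | R², change in severity, if it were measured | Ratio (1 − rho)/2 |
|---|---|---|---|---|
| 0.3 | 0.102 | 0.292 | 0.292 | 0.35 |
| 0.5 | 0.063 | 0.250 | 0.250 | 0.25 |
| 0.7 | 0.028 | 0.188 | 0.188 | 0.15 |
| 0.8 | 0.014 | 0.143 | 0.143 | 0.10 |
| 0.9 | 0.004 | 0.083 | 0.083 | 0.05 |

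Example at rho 0.5: Var(dQ) = 2 + 4 × 0.5 = 4; baseline severity 0.25/4 = 0.063; change in symptoms 1/4 = 0.25. A simulation with 200,000 subjects gave ratios of 0.353, 0.248, 0.152, 0.097 and 0.047.

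For any rho of zero or more the ratio is at most one half, so in this model rho sets the size of the tilt and not its direction. When both factors enter as changes, or both as baseline values, the shares are equal. The gap therefore comes from the form of entry.

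**Question 2, same model.** The slope on change in symptoms has size 1 at every visit. The slope on baseline severity has size 1 − rho: 0.10 at rho 0.9, 0.50 at rho 0.5, 0.70 at rho 0.3. If correlation with baseline decays over follow-up, that slope grows. The hypothesis predicts that unmodifiable associations will decrease, so Question 2 is not tilted towards its own hypothesis.

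**Question 2, wording against model.** The question speaks of changes in unmodifiable factors. The model takes over the Question 1 predictors, where demographics and severity are baseline values, and adds interactions with time. No 3- or 6-month ejection fraction or BNP is scheduled, so a change-on-change association across the three visits is not available for them. The fitted model answers a baseline-by-time question.

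**The case against.** The strongest reply is that Question 1 openly states which predictors are baseline values and which are changes, and that it asks how much changes in modifiable factors explain. A change-on-change share answers that. The size of the gap depends on equal weights, shared dynamics and stationarity, none of which the protocol supports with a figure. The widest gap also arises at high rho, where a factor that barely moves ought to explain little of a change.

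Much of this stands. The share for modifiable changes is a legitimate quantity, and the fold differences are not estimates for this trial. What remains is that the hypothesis is a ranking across blocks. Stability does not account for the whole gap either: within severity alone, R²(baseline S) / R²(change in S) = [(1 − rho)²] / [2(1 − rho)] = (1 − rho)/2, whatever the dynamics of symptoms. Low movement can make the severity share truly small, and baseline-only entry shrinks it further.

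A reader might also infer stronger points that the protocol does not support:

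- *Question 1 needs repeat ejection fraction and BNP.* It does not; it specifies baseline values.
- *Question 2 cannot be run.* It can; its method only adds time interactions to the Question 1 models. The protocol also never labels ejection fraction and BNP as unmodifiable; that is an inference.
- *These markers are never collected, or never repeated.* They are recorded at enrollment. Table 6 marks the Study Form again at 12 months, so a second value is not described but not excluded.
- *The predicted answers are guaranteed.* Question 1 is tilted, by an unknown amount, and Question 2 is not tilted towards its hypothesis.

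**Conclusion.** The point holds for Question 1 as a structural tilt. With two equally important, independent, stationary factors, the one entered only at baseline explains (1 − rho)/2 as much of the change in quality of life as the one entered as a change. That is 35% at rho 0.3, 25% at 0.5 and 5% at 0.9, or a gap of roughly 3- to 20-fold (1/0.35 to 1/0.05). These values illustrate direction and possible scale; rho in this population is not given. The planned variance shares cannot be read as the relative importance of disease severity and modifiable factors.

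The mismatch between wording and model in Question 2, and the predictor without an instrument in Question 1, are real but close to clerical. Everything here is exploratory, and the primary endpoint is unaffected. Priority is low.

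**What to change.** 1. **Question 1 reporting.** Report the change-on-change share as the answer to how much changes in modifiable factors explain. State that it will not be ranked against baseline-only ejection fraction and BNP, nor read as relative importance.
2. **One added model.** Compare the variance in quality-of-life change explained by baseline severity with that explained by baseline modifiable factors (MSAS-SF, PHQ-9, FACIT-Sp). Say that this addresses prediction of later change, which is a different question from item 1.
3. **Question 2 wording.** Refer to baseline unmodifiable factors, to match the stated model and the absence of any 3- or 6-month ejection fraction or BNP.
4. **Predictor list.** Delete attitudes about impairment, or name the collected scale that is meant.

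The cost is some wording and one extra exploratory model on data already scheduled for collection. The expected message that modifiable factors dominate may come out weaker.

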#### Overview

[figure not shown]
Previous observational studies demonstrate aspects of the conceptual model (Figure 1), but no intervention studies have examined these relationships. The *objective* of this aim is to understand longitudinal relationships between symptoms, depression, and quality of life. *We are not powered to examine direct intervention effects*

on quality of life, but, as supported by a vast literature on mediation analysis, we are adequately powered to examine mediational pathways by which the intervention influences quality of life (see "power analysis" below). We will test the hypothesis that symptom experience, measured as symptom severity using the ESAS total score, and the number of depressive symptoms, measured by the PHQ-9 score, mediate the relationship between the intervention and health-related quality of life, measured by the KCCQ quality of life subscale. This hypothesis will be tested using a structural equation modeling framework because the variables are measured longitudinally, and we are interested in testing mediation pathways and using multiple dependent variables. The rationale for this aim is that a fundamental understanding of the relationships between symptoms, depression, and quality of life is critical to the further refinement of therapeutic strategies to improve symptoms and quality of life. For example, we will understand the relative importance of each path of intervention effect, and consider strengthening or diminishing the palliative symptom management or psychosocial care components. If the intervention is not successful, a deeper understanding of the relationships between these variables will guide the content of future interventions to improve symptoms and quality of life. Furthermore, examining these variables in a longitudinal study will provide much stronger evidence for their relationships.

Data Analysis Plan

The analyses for this aim will be carried out using Mplus following well-established statistical methods for testing the mediated effect with longitudinal data and multiple mediators. The general structure of the proposed model is depicted in Figure 3. This model is a simplified version of the overall conceptual model (Figure 1). The model will be estimated in a parallel process growth modeling framework where the change in symptom severity over time will be estimated simultaneously with the change in the number of depression

Figure 3. Structure of the mediational model

symptoms over time, each of which will be captured by latent initial status and slope factors. The a1 path from the intervention to symptom severity will measure the impact of the intervention on changes in symptom severity (the symptom severity slope factor) and the a2 path will test the impact of the intervention on changes in the number of depression symptoms (the depression slope factor). The b1 path from depression to symptom severity is included to test the hypothesis that some of the impact of depression on quality of life will occur through reduced symptom severity. The b2 and b3 paths capture the effects of the symptom severity and depression slope factors on health-related quality of life measured at the end of the study. The overall fit of the proposed model, the significance of the individual paths, and the significance of the mediated effects will be assessed. The mediated effects will be calculated using the product of coefficients method and will be evaluated for statistical significance by a bias-corrected bootstrapped standard error estimate. Three specific indirect effects will be estimated: (1) the indirect effect of the intervention on health-related quality of life through symptom severity (a1\*b2), (2) the indirect effect on quality of life through depression (a2\*b3), and (3) the indirect effect on health-related quality of life in a multiple mediator framework through the intervention's impact on depression and the impact of depression on symptom severity (a2\*b1\*b2).

Through exploratory analyses, we will examine the same model using our alternative measures of the symptom experience (symptom distress, GSDS) and health-related quality of life (QUAL-E subscales).

Aim 2 Power Analysis

Power calculations were based on the magnitude of the individual paths, as well as the power to test each of the three proposed specific indirect effects. Power was calculated in Mplus using a Monte Carlo simulation.

 The population model followed the structure of Figure 3, but was estimated as a parallel process growth model. For consistency with the power estimates under Aim 1, moderate-sized effects from the intervention to symptom severity and depression were specified (i.e., 13% of the variance in symptom severity and depression accounted for by the intervention). Based on an earlier cross-sectional study showing large correlations (>.50) between symptoms, depression, and quality of life, large effects (26% of the variance in outcomes) were specified for the paths from depression to symptom severity, from depression to health-related quality of life, and from symptom severity to quality of life. Assuming a two-sided  $\alpha = .05$ , power was sufficient ( $\geq .80$ ) to detect significant differences in each of the paths and in the three mediated effects. Power estimates may be considered conservative because Monte Carlo simulations do not calculate power using bootstrapped estimates, although this method has been shown to be the most powerful method for testing the significance of the mediated effect and will be used in this analysis.

**Aim 3. Examine the effect of the intervention on informal family caregivers' depression, burden, benefit-finding, social support, perceptions of patients' symptoms, quality of the patient-caregiver relationship, and contributions to patients' heart failure self-care.**

Similar to Aim 1, analyses of the repeated measures will be performed using maximum likelihood estimation (MLE) for incomplete data (SAS Proc Mixed) to examine the differences between caregivers of patients in the intervention compared to caregivers of patients in the control group over time on caregivers' depression, burden, benefit-finding, perceptions of patients' symptoms, quality of the caregiver-patient relationship, and contributions to patients' heart failure self-care.

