**Specific Aims:**

Aim 1. Assess the effect of a symptom management and psychosocial care intervention on heart failure-specific health status as a primary endpoint, and symptom distress, depression, quality of life, self-care, and spiritual well-being as pre-specified secondary endpoints.

Aim 2. Evaluate whether the intervention influences quality of life indirectly through effects on symptom distress and depression.

Aim 3. Examine the effect of the intervention on informal family caregivers' depression, burden, benefit-finding, social support, perceptions of patients' symptoms, quality of the patient-caregiver relationship, and contributions to patients' heart failure self-care.

Aim 4. Identify valuable core CASA intervention content and processes from the perspectives of patients and intervention team members.

Aim 5. Identify barriers and facilitators to the implementation and sustainability of CASA from the perspectives of providers (i.e., physicians, nurse practitioners) whose patients received the CASA intervention.

Aim 6. Determine interest and capacity of rural clinic settings to adopt CASA's team-based model of outpatient palliative and psychosocial care.

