Data will be collected and analyzed to assess the intervention effects on patients (Aim 1), conduct the mediation analysis (Aim 2), the intervention effects on informal caregivers (Aim 3), evaluate intervention content and process (Aims 4-5) and determine interest in program and implementation capacity of rural providers (Aim 6) utilizing the following methods.

Patient Outcome Measures and Planned Study Visits (Aims 1-4)

Research assistants will administer measures to patients during four study visits: enrollment (baseline), 3, 6, and 12 months (Table 6). The estimated completion time is 45-50 minutes with an additional 15 minutes for intervention patients who complete the evaluative interview. The measures were chosen to reflect domains of the conceptual model (Figure 1) as follows (instrument abbreviations defined below):

- **Antecedents:** Left ventricular ejection fraction, brain natriuretic peptide (BNP), demographics, cognitive status (TICS)
- **Symptom Experience:** MSAS† (symptom severity), GSDS† (symptom distress), PEG, PROMIS fatigue, dyspnea assessment
- **Depression:** PHQ-9†
- **Health-Related Quality of Life:** KCCQ quality of life subscale\*, QUAL-E§, EQ-5D†; FACIT-Sp†
- **Other:** SCHFI†, Mutuality Scale¥, ESSI¥, Satisfaction†

\* Primary endpoint measure (Aim 1)

† Secondary endpoint measure (Aim 1)

§ Measure used in Aim 2 mediational model

¥ Measure used in Aim 3

Table 6. Study Visits and Assessments for Aims 1-4	Baseline	3-Month	6-Month	12-month
Assessment				
Questionnaires/surveys	X	X	X	X
Demographics/Study Form	X			X
Medications	X	X	X	X
Hospitalizations/mortality		X	X	X
Program evaluation (intervention only)			X	

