**Table 7. Study measures to be completed by patient participants for Aims 1-4.**

Conceptual Model Domain (Figure 1)	Measure	Number of Items	Completion Time
Antecedents			
Situational, sociodemographic, and physiological factors	Demographics	10	5 minutes
Cognitive Status	TICS	11	4 minutes
Decision Making	Control Preferences Scale	1	< 1 minute
Symptom Experience			
Symptom distress	MSAS-SF	13	3 minutes
Symptom Distress	GSDS	1	< 1 minute
Pain intensity and interference	PEG	3	1 minute
Fatigue intensity and interference	PROMIS Fatigue	8	2 minutes
Breathlessness intensity and interference	Dyspnea Assessment	3	1 minute
Depression/Anxiety			
Depression	PHQ-9	10	3 minutes
Anxiety	GAD-7	7	2 minutes
Health-related Quality of Life			
Health Status	KCCQ	23	8-10 minutes
Spiritual Well-Being	FACIT-Sp	12	5 minutes
Quality of Life	QUAL-E	16	8 minutes
Health Status	EQ-5D-5L	6	3 minutes
Disability	Sheehan Disability Scale	5	2 minutes
Other			
Self-care	SCHFI	22	8-10 minutes
Relationship Quality	Mutuality Scale (for patients with informal, family caregivers only)	15	5 minutes
Satisfaction with Healthcare	Recommend Healthcare to Others	3	< 1 minute
Program evaluation (Intervention only)	Qualitative evaluation questions	7	15 min

Formatted Table

1. **KCCQ (Primary endpoint):** The Kansas City Cardiomyopathy Questionnaire is a 23-item self-administered questionnaire (administration time 5-10 minutes) that measures HF-specific health status. Validated subscales measure HF symptom burden and quality of life. The KCCQ is reliable, sensitive to clinical change, and predicts hospitalization and mortality. The single depression item will be removed from analysis of the quality of life subscale given measurement overlap with the PHQ-9.

2. **MSAS-SF:** The Memorial Symptom Assessment Scale is a valid and reliable self-report measure of symptom distress. Patients check off which of 10 symptoms (e.g., pain) they have had over the past week. Patients who have had the symptom rate how much that symptom distressed or bothered them from 0 ("not at all") to 4 ("very much") on a numeric rating scale. The primary endpoint will be the sum of the three symptoms the trial is targeting (pain, lack of energy, and shortness of breath) and a secondary endpoint will be the sum of the other symptoms, because the intervention will most likely affect them but they are not directly targeted.

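### The Aim 2 mediation model takes its symptom mediator from ESAS, an instrument the trial does not collect; a named MSAS-SF score should replace it

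*Protocol*

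**What the plan says.** All references are to the Protocol; no statistical analysis plan was available.

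- **Mediator.** The Aim 2 Overview hypothesises that symptom experience, "measured as symptom severity using the ESAS total score", and PHQ-9 depression mediate the effect of the intervention on the KCCQ quality of life subscale.
- **Data source.** The Aim 2 statement in the Data Analysis Plan says: "The data gathered in the clinical trial described in Aim 1 will be used to complete this aim".
- **Measures collected.** Patient Outcome Measures and Planned Study Visits (Aims 1-4) lists MSAS under symptom experience, labelled symptom severity. The entry then continues with GSDS and the remaining scales: "symptom distress), PEG, PROMIS fatigue, dyspnea assessment". Table 7, titled "Study measures to be completed by patient participants for Aims 1-4", has the same five symptom instruments. Table 6 schedules the questionnaires at baseline, 3, 6 and 12 months.
- **Content of MSAS-SF.** Under measure 2, patients who have had a symptom "rate how much that symptom distressed or bothered them". Two scores are defined: a sum of the three targeted symptoms and a sum of the others.
- **Wording of the aim.** Specific Aims reads "Evaluate whether the intervention influences quality of life indirectly through effects on symptom distress and depression". The Data Analysis Plan restates the same aim with symptom severity in place of symptom distress.
- **Alternatives.** The Aim 2 Data Analysis Plan reserves GSDS, labelled symptom distress, and the QUAL-E subscales for exploratory re-runs of the model.

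**The concern.** A mediation model needs a measured mediator. If the protocol specifies one that is not on its own measurement schedule, the analysis cannot be carried out as specified, and someone must later decide what to use instead. A decision made after outcome data by arm have been seen would weaken tests of specific indirect effects. Aim 2 is a numbered aim. Limitations and Considerations relies on it to judge the relative importance of the intervention components, and Knowledge to be Gained and Future Directions relies on it when deciding how to modify the intervention.

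**Working it through.** No stated figure is in dispute, so the check sets the sections side by side.

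**1. Where ESAS appears.** It is named once, in the Aim 2 Overview, and is never spelled out or described. It is absent from:
- the domain list in Patient Outcome Measures;
- Table 7;
- the numbered patient measure descriptions (1 to 20);
- the caregiver measures and Table 8.

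Because Aim 2 draws only on Aim 1 data, no other collection could supply it.

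**2. What depends on it.** The Aim 2 Data Analysis Plan names five paths:

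| Path | From | To | Needs the symptom score? |
|---|---|---|---|
| a1 | intervention | symptom slope | yes |
| a2 | intervention | depression slope | no |
| b1 | depression | symptom severity | yes |
| b2 | symptom slope | quality of life | yes |
| b3 | depression slope | quality of life | no |

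Three of the five paths need it. Of the three indirect effects, a1*b2 and a2*b1*b2 pass through it, which is two of three. The third, a2*b3, uses PHQ-9 and the KCCQ quality of life subscale, both collected. It is nevertheless specified inside the same joint parallel-process model, which includes the symptom factor.

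**3. What the protocol points to instead.** The domain list assigns severity to MSAS and distress to GSDS. The Aim 2 Data Analysis Plan has the same split, with severity in the main model and GSDS distress as the alternative. On the protocol's own labels, MSAS belongs in the main-model position. It covers several symptoms and is collected at all four visits.

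**4. Why MSAS still does not settle it.**
- Table 7 and the MSAS-SF description call the instrument symptom distress, against the severity label in the domain list.
- ESAS was to enter as a total score. The MSAS-SF description defines a three-symptom sum and a sum of the rest, but no total.
- The description speaks of 10 symptoms, while Table 7 lists 13 items, so the item set of any total is uncertain.

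**5. Aim 2 power inputs.** The Aim 2 Power Analysis specifies 13% of variance for the intervention paths and 26% for the paths among depression, symptoms and quality of life. Neither share is tied to ESAS. The claimed power of at least .80 cannot be reproduced, because the growth-model parameters are not given; this point does not depend on it.

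**6. Aim 1, as background.** The Sample Size section concerns the KCCQ overall score and does not use ESAS. Its figure reproduces: 312 × (1 − 0.25) / 2 = 117 per arm. With an effect of 0.4 SD and two-sided α = 0.05, power is 86.4% by the normal approximation and 86.1% by the t distribution, against the stated 86%.

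**The case against.** The strongest reply is that ESAS is simply an instrument name left unrevised. The domain list labels MSAS as severity, the Aim 2 model is about severity, and MSAS-SF is collected at every visit. On that view nothing is missing except a corrected name, and choosing between MSAS-SF sums is a scoring detail that an analysis plan may already fix.

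Much of this stands, and it rules out several stronger readings:

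- **That there are no symptom data behind the model.** A multi-symptom instrument is collected at all four visits. The mediator is misnamed and its exact score unspecified, which is a smaller fault.
- **That the substitute is wide open.** PEG, PROMIS Fatigue and the Dyspnea Assessment each cover one symptom and are not natural stand-ins for a multi-symptom total. GSDS already has the exploratory role.
- **That a post hoc choice will follow.** An analysis plan not seen here may fix the score, so this is a risk and is not established.
- **That the QUAL-E footnote is wrong.** QUAL-E carries the mark "Measure used in Aim 2 mediational model", and it is used in an exploratory version of that model. The mark is true.
- **That another unmeasured construct widens the fault.** The phrase "attitudes about impairment and spiritual well-being" belongs to exploratory Question 1 under Aim 1 and has no bearing on the Aim 2 model.
- **That the power simulation must be repeated.** Its stated effect inputs are generic variance shares, so renaming the instrument changes none of them.

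What the reply does not remove is that the protocol names a specific instrument and contradicts its own list of measures. Deferral to an analysis plan does not explain that. Nor does the severity label on MSAS identify a score, given the distress description and the lack of a defined total.

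**Conclusion.** The point holds in limited form. The main Aim 2 model cannot be run as written: three of five named paths and two of three indirect effects rest on an instrument outside the measurement schedule. The protocol's labels largely indicate MSAS-SF as the replacement. What remains open is which MSAS-SF score to use and whether it is to be called severity or distress.

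This should be fixed, but it is not critical to the trial. The Aim 1 primary endpoint, its analysis and the sample size do not use ESAS. The conclusion assumes that the measure lists in the protocol are complete. It makes no judgement on whether the variance shares in the Aim 2 Power Analysis are realistic, which is a separate question.

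**What to change.** Before outcome data by arm are examined:

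1. In the Aim 2 Overview, replace the ESAS total with one named MSAS-SF score. Either use the three-targeted-symptom sum already defined under measure 2, or define an all-symptom total, list its items and resolve the 10-symptom versus 13-item conflict.
2. Keep GSDS as the exploratory alternative.
3. Reconcile the severity and distress wording across Specific Aims, the domain list in Patient Outcome Measures, Table 7, the MSAS-SF description, and the Aim 2 statement, Overview and Data Analysis Plan.
4. State in the Aim 2 Power Analysis that the 13% and 26% variance assumptions are taken to apply to the chosen score.

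The cost is a wording amendment. No instrument is added, no new data are collected, and repeating the simulation is optional.
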